Data from recent studies, including our own (2), show that GLP-1RA can lower blood glucose concentrations in patients with type 1 diabetes through their protean actions, independently of the beta cell. These actions include suppression of appetite and carbohydrate intake, slowing of gastric emptying and the suppression of glucagon. Our recent work has shown that liraglutide not only markedly suppresses the post prandial excursion of glucagon, it also suppresses fasting plasma FFA concentrations (Fig 1). In this context, it is important that the deletion of the glucagon receptor protects both from hyperglycemia and ketosis following a high dose of streptozotocin in mice (10). Therefore, it is possible that GLP-1 mimetics may protect from DKA in presence of sufficient insulin.

SGLT-2 inhibitors are of special importance since their mode of action is independent of insulinogenesis. They are selective antagonists to sodium-glucose transporter in the proximal convoluted tubules in the kidneys. They act by inhibiting glucose re-absorption in the renal tubules and thus inducing the excretion of 60-100 grams per day of glucose in urine (7). They have been studied extensively for use in type 2 diabetes however; there is still paucity of data regarding any benefits in type 1 diabetes. Recent studies have shown that they have similar effects of enhanced 24 hour urine glucose excretion in type 1 diabetes, just like in patients with type 2 diabetes with improved glycemic indices. Indeed, Mudaliar et al (3) demonstrated that use of remogliflozin in patients with type 1 diabetes significantly reduced glucose concentrations relative to a placebo after a standard glucose load and glucose improvements were sustained for up to 10 hours. Perkins et al (6) studied use of 8 weeks of empagliflozin in type 1 diabetes and demonstrated significant reduction in HbA1c, fasting blood glucose, the rate of hypoglycemia and the daily insulin dose. Mean urinary excretion of glucose increased and significant weight loss was observed. Cherney et al(1) also demonstrated significantly increased glucose excretion and fall in HbA1c despite lower insulin doses with use of empagliflozin 25mg daily for 8 weeks in patients with type 1 diabetes.

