dapagliflozin 10mg (two 5mg) with appropriate placebos in a randomized fashion). Subjects will be fasting throughout the first 6 hr of the visit. Blood (10ml) will be collected every 30 min and spot urine every 1hr for up to 8 hours. Additional blood samples (20ml) will be collected at 1, 2, 4 and 6 and 8 hours for *MNC* isolation. A second adipose tissue biopsy will be collected at 360 min after starting the treatment. Basal insulin Infusion will be restarted at the end of the 360min sample collections, food will be provided, patient will be instructed to deliver a bolus insulin dose through bolus wizard calculator of the insulin pump after entering the grams of carbohydrates and blood glucose (Bolus wizard matches the bolus insulin dose based on individual patient's insulin to carbohydrate ratio and correction factor for high blood glucose). Patients will be monitored for at least 2hr before discharging from center (8hr time point). The subject's blood glucose and ketones ( $\beta$ -hydroxybutyrate) levels will be monitored every 30 minutes and ketones will be also measured in urine using Ketostix every hour to ensure safety. If the BG concentrations exceed 400 mg/dl or blood  $\beta$ -hydroxybutyrate exceeds 2.5mmol/l (or +3 (80mg/dl) or greater in urine) anytime during the 360 minutes following single dose/doses with or without clinical signs and symptoms of DKA like nausea and vomiting then STAT lab sample for CMP will be collected along with research blood sample. Spot urine and adipose tissue biopsy will be collected only if deemed feasible by the investigator present based on the clinical condition of the participant. Basal insulin will be restarted; bolus insulin as per the bolus wizard calculator will be administered and a meal provided. Patient will be discharged only after all laboratory parameters return to pretesting levels with no clinical symptoms of DKA.

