### **Procedures:**

1. **Ketone bodies measurements:** Serum and plasma samples will be collected from whole blood within 30 min and stored at -80C till analysis. Spot and 24 hr urine samples will be centrifuged and clear supernatant stored at -80C till analysis. Plasma and urine samples will be analyzed for ketone bodies using commercially available kits for  $\beta$ -hydroxybutyrate (Cayman Chemicals, Ann Arbor, MI) and for acetoacetate (Biovision, Malpitas, CA). Patients will be instructed to measure ketone bodies in urine samples daily with Ketostix (Bayer).
2. **MNC isolation:** Blood samples (30-40ml) is collected in Na-EDTA and carefully layered on Lympholyte medium (Cedarlane Laboratories, Hornby, ON) according to manufacturer's instructions. Samples are centrifuged and two bands separate out at the top of the RBC pellet. The MNC band was harvested and washed twice with Hank's balanced salt solution (HBSS). This method provides yields greater than 95% MNC preparation.

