The secondary end points include the *comparison of the acute changes in AUC0hr-6hr of ketone bodies (plasma and urine), FFA and glucagon between dapagliflozin, exenatide, combination of both and placebo before and after 12 weeks of treatment period using Paired t-test for within group comparisons and student t-test for between groups comparisons.* Additional secondary end points include comparison of basal plasma glucagon, FFA and urinary ketone bodies changes after 12 weeks of dapagliflozin and Bydureon or combination of both treatments compared to baseline using paired t-test and to placebo using 2-way RMANOVA. Changes in insulin dose, glucose levels and carbohydrate intake will be compared after 12 weeks of dapagliflozin and Bydureon treatments to baseline using paired t-test and to placebo with 2-way RMANOVA. Changes in lipolysis mediator (HSL) in plasma and expression of HSL and SGLT-2 in adipose tissue and MNC will be compared to baseline using paired t-test and to placebo with t-test.

*17.2 If applicable, provide a power analysis.*

*NOTE: This may not apply to certain types of studies, including chart/records reviews, survey studies, or observational studies. This question is asked to elicit whether the investigator has an adequate sample size to achieve the study objectives and justify a conclusion.*

*Response:* Conservatively estimating a difference in the change from baseline in ketone bodies generation between the dapagliflozin and placebo of 50%, with standard deviation of no more than 50%, a sample size of 20 patients per group (assuming a drop-out rate of 15%) should provide adequate power ( $\beta = 0.2$ ) to detect a significant difference ( $\alpha = 0.05$ ). A total of 80 patients will be recruited for the study.

*17.3 Describe any procedures that will be used for quality control of collected data.*

*Response:* Data will not be imputed to replace missing data and only observed data will be used to run the mixed model for repeated measurement (MMRM) analysis

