### **Risks Associated with Administration of study drugs:**

All subjects will be referred to Bydureon (extended release exenatide) and dapagliflozin labeling safety information, and will be provided a copy of the package insert of the medication. Discussion of the potential side effects and the different warning and precautions will take place at the time of signing the informed consent and prior to treatment. **Patients will be informed they must not discontinue their insulin during the study.**

Potential side effects of GLP-1 agonist and SGLT-2 inhibitors include hypotension, nausea, polydipsia, polyuria, dehydration, reduced GFR. Patients will be provided guidance on potential side effects and how to properly manage and report it. The potential benefits including improved glycemia, improved BP, potential renal protection, improved quality of life (QOL) will most probably overcome the potential side effects.

Bydureon caused rats to develop tumors of the thyroid gland. Some of these tumors were cancer. It is not known if Bydureon will cause thyroid tumors or a type of thyroid cancer called medullary thyroid cancer in people. This will be discussed in details with all participating subjects. Exenatide is contraindicated in patients with a personal or family history of MTC and in patients with Multiple Endocrine Neoplasia syndrome type 2 (MEN 2).

Injection-site reactions: Serious injection-site reactions, with or without bumps (nodules), have happened in some people who use BYDUREON. Some of these injection-site reactions have required surgical intervention. Report any injection site reactions including nodules to study investigators.

All the known adverse effects with SGLT-2 inhibitors will be discussed with patients before the start of the study as follows:-

- Intravascular volume contraction and symptomatic hypotension can occur after initiating SGLT-2 inhibitors.
- Impairment in Renal Function - SGLT-2 inhibitors increases serum creatinine and decreases eGFR. Elderly patients and patients with impaired renal function may be more susceptible to these changes.
- Genital mycotic Infections - SGLT-2 inhibitors increases the risk of genital mycotic infections. Patients with prior history were more likely to develop genital mycotic infections.

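### The urinary ketone AUC rests on hourly spot urine with no void volume or creatinine, so it depends on urine flow, which may differ by arm

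*Combined protocol and SAP*

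**What the plan says.** Section 17.1 lists among the secondary endpoints the acute change in AUC from 0 to 6 hours "of ketone bodies (plasma and urine), FFA and glucagon between dapagliflozin, exenatide, combination of both and placebo", before and after the 12 weeks of treatment. The tests are "Paired t-test for within group comparisons and student t-test for between groups comparisons". No unit is given for the urine AUC.

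The sampling is in Section 10.1, Visit 2: "Blood (10ml) will be collected every 30 min and spot urine every 1hr for up to 8 hours". Visit 6 repeats it, and at both visits only pump patients go through the acute test. The laboratory step is in Section 10.1, Procedures, item 1: "Spot and 24 hr urine samples will be centrifuged and clear supernatant stored at -80C till analysis", followed by "Plasma and urine samples will be analyzed for ketone bodies using commercially available kits for" beta-hydroxybutyrate and acetoacetate. Section 10.2 adds only that ketones are measured in every urine sample.

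Separately, 24-hour urine is brought to Visits 2 to 6. Section 17.1 also compares the 12-week change in basal urinary ketones with baseline and with placebo. It does not say whether that comparison uses spot or 24-hour urine, or whether it uses a concentration or an amount.

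Sections 2.1, 10.1, 10.2 and 17.1 contain no void volume, 24-hour volume, urine creatinine, excretion rate or instruction to empty the bladder at time 0.

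**The concern.** A kit assay on a spot sample returns a concentration, which is ketone output divided by urine flow. Its integral over six hours is not an amount excreted. If flow is the same in all arms, that costs only precision. If flow differs by arm, the urine comparison mixes ketone output with dilution.

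The documents give a reason to expect that flow may differ. Section 3.1 describes SGLT2 inhibitors as "inducing the excretion of 60-100 grams per day of glucose in urine", and the potential side effects that Section 21.1 lists for the two study drug classes are "hypotension, nausea, polydipsia, polyuria, dehydration, reduced GFR". Extra flow in the dapagliflozin-containing arms would lower their urine ketone concentration relative to placebo and could mask a rise in excretion. The paired comparison of the day 0 and week 12 tests is open to the same problem if flow changes over treatment.

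What is at stake is the urine part of Aim 1.1. If plasma and urine disagreed, the trial would have no data to tell a real difference in ketone handling from dilution. A volume that was not recorded cannot be recovered at the analysis stage.

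**Working it through.** **The plan's own figures.** No power figure is given for the urine AUC. Section 17.2 covers the dapagliflozin-placebo contrast in ketone change: difference 50%, SD 50%, alpha 0.05, power 80%, 15% drop-out, 20 per group. Taking alpha as two-sided, the exact t-test needs 16.7, so 17 per arm, and 17 / 0.85 = 20. The stated figure reproduces and is not in dispute. The 50% is borrowed below as an illustrative true rise in urinary excretion.

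**Formula.** Let E be the true ratio of ketone excretion (dapagliflozin to placebo) and V the ratio of urine volume over the same period. Then

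observed concentration ratio = E / V.

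The documents give no urine volumes, so V is an assumption, shown over 1.0 to 1.5.

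| Assumed V | E = 1.5 reads as | Change seen | E = 2.0 reads as | Illustrative power for E = 1.5 |
|---|---|---|---|---|
| 1.0 | 1.5 / 1.0 = 1.50 | +50% | 2.00 | 0.81 |
| 1.1 | 1.5 / 1.1 = 1.36 | +36% | 1.82 | 0.54 |
| 1.25 | 1.5 / 1.25 = 1.20 | +20% | 1.60 | 0.205 |
| 1.5 | 1.5 / 1.5 = 1.00 | 0% | 1.33 | 0.05 (alpha) |

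A rise cancels completely when V equals E. If V were below 1, the rise would be exaggerated.

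**Reading the power column.** It uses a two-sample t-test with 17 completers per arm and SD 50%, both taken from Section 17.2, whose primary outcome is plasma. It shows how quickly a dilution effect would use up power; it is not a forecast. The numbers are optimistic, because only pump patients enter the acute test and, under Section 4.1, only cohort 1 has a placebo arm, with 15 patients.

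**With an amount-based endpoint.** Concentration x volume gives E directly, so the 50% difference is kept whatever V is.

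**The case against.** The strongest reply is that the plan never says urine is analysed as a concentration; it simply gives no unit. That is true. The reading comes from three facts together: spot samples, kit assays, and no volume or creatinine anywhere. If volumes are recorded in practice, the remedy is to write that down. But a team following the text as it stands would have nothing except concentrations to integrate.

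A reader might infer that dapagliflozin's diuresis will bias the acute comparison against Hypothesis 1 by a calculable amount. For example, assumed daily volumes of 1.5 to 2.0 L with an extra 0.3 to 1.0 L give concentration ratios of 2.0/2.3 = 0.87 down to 1.5/2.5 = 0.60, a fall of 13% to 40%. The documents do not support carrying this over to the acute endpoint. That endpoint is a six-hour fasting test after a single dose with insulin stopped, and Visit 2 provides for glucose above 400 mg/dl, so placebo patients may have an osmotic diuresis too and V may be close to 1. Section 21.1 lists polyuria for both drug classes jointly and lists dehydration beside it; Section 3.1 gives grams of glucose and no urine volume.

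A reader might also infer that the basal 12-week urine comparison is biased. That is not shown: a 24-hour collection is the right sample for total excretion, and the plan does not say how the result will be expressed.

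Two further points stand. Section 17.1 cites a more than two-fold rise in total ketones in preliminary data (on a liraglutide background); a doubling would still read as 1.33 at V = 1.5, so it would be reduced but not hidden. And plasma ketones are sampled every 30 minutes in the same test, so Hypothesis 1 can be tested without urine.

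**Conclusion.** The point holds as a weakness in a secondary measure. As written, the urine AUC depends on urine flow, in a trial of a drug that the protocol itself describes as glucosuric, and nothing is collected that would allow a correction or even show whether one is needed. Dilution could differ by arm and could mask a rise in ketone excretion; neither its size nor its direction in the acute test follows from the documents. The +50% down to 0% reading of a true 50% rise rests on an assumed volume ratio of 1.0 to 1.5 and is an illustration only.

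The basal urine comparison has the same exposure only if spot or 24-hour urine is analysed as a concentration. The primary endpoint, fasting plasma ketones, is unaffected, as are the plasma AUCs. The change is worth making because it is cheap and the missing volumes cannot be reconstructed later.

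**What to change.** 1. **Section 10.1, Visits 2 and 6.** Make the time 0 urine sample a complete void, and record the volume of each hourly void. Record the total volume of every 24-hour collection (Visits 2 to 6).
2. **Section 17.1, acute urine endpoint.** Replace the urine AUC with cumulative ketone excretion over 0-6 h: concentration x volume for each void, summed.
3. **Section 17.1, basal urine comparison.** State that it uses total ketone excretion per 24 hours.
4. **Sensitivity analysis.** Measure creatinine on the stored urine of all patients and report the ketone/creatinine ratio as one consistent analysis. Where volumes were not recorded, make the ratio the main urine measure for everyone. Do not mix ratios and amounts in one endpoint, since their units differ and they cannot be summed. Section 21.1 names reduced renal function as a drug effect, which is a further reason to prefer the amount where volumes exist.

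**Cost.** Up to eight hourly volumes per acute test, five container volumes per patient, complete emptying at each void, and a routine creatinine assay. No new visit or sample is needed. Urine supernatant is stored at -80C and Section 18 keeps specimens for at least 7 years, so creatinine can also be added to urine already collected.

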In the acute effects study, qualified patients will come fasting to the research center. Review of study procedures and vitals will be performed. Insulin infusion (pump) will be stopped and basal blood, urine and adipose tissue biopsy samples will be obtained. Placebos, exenatide (5µg) or dapagliflozin (10mg) (with appropriate placebos) or combination of exenatide and dapagliflozin will be administered, according to a randomized fashion and cohort assigned, and blood samples will be collected every 30 min for up to 8 hours after starting the treatment. Urine will be collected every hour up to 8 hours and a second adipose tissue biopsy will be collected at 6 hours after the start of the treatment. Additional blood samples will be collected at 1, 2, 4 and 6 and 8 hour marks for MNC isolation. Plasma and mononuclear cell (MNC) fractions will be prepared from the blood samples. The patient will then come back at the 24 hour mark for a fasting blood and urine collection. The long term study will then commence. Depending on the cohort, Exenatide extended release or dapagliflozin (along with appropriate placebos) or a combination of both drugs will be started and continued for 12 weeks according to original randomization of day 0. In the long term study, dapagliflozin (or the appropriate placebo) will be started at 5mg dose and will be titrated to 10mg/day after 5 days. Fasting blood and 24hr urine samples will be collected at 1, 4 and 8 weeks. At 12 weeks, the 2nd acute effects testing study will be repeated as described above.

Drug Blinding:

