#### *Response:*

Measurements of beta-hydroxybutyrate, acetoacetic acid, glucose, FFA and glucagon, will be measured from all blood samples collected. HSL, GLP-1, glycerol, electrolytes, serum bicarbonate, cortisol and catecholamines will be measured at 0, 60, 120, 240, 360, 480 min and at 24hr following single dose studies at 0 and 12 weeks visits and at baseline on the 1, 4 and 8 weeks visits. Ketone bodies will be measured in all urine samples. All MNC and adipose tissue samples will be tested for HSL and SGLT2 expression, as in the table below.

Visit #	Screening	1	2	3	4	5	6
Day #		-7	0	8 week 1	28 week 4	56 week 8	84 week 12
Study Procedures	Screening	Insulin titration	Single dose test	2 days after up titration			End long term/ Single dose test
History	X						
Physical	X				X		X
CBC	X						X
CMP/lipid profile	X				X		X
Vitals and BP	X	X	X	X	X	X	X
Pregnancy test	X				X	X	X
HbA1c	X						X
Plasma ketone bodies and metabolic end points			X	X	X	X	X
Urine ketone bodies and oxidative stress end points			X	X	X	X	X
Insulin injection log/Glucose/CGM/pump and food diary review/Insulin dose titrations		X Review of glucose/Insulin doses	X	X	X	X	X
Adipose tissue biopsy			X				X

 10.3 List any instruments or measurement tools used to collect data (e.g. questionnaire, interview guide, validated instrument, data collection form).

*Include copies of these documents with your submission.*

Response: Source documents will be used to collect patient information. The CGM or insulin pump will be used to collect glucose and insulin data, Glucose and ketone meter will be used to measure glucose and ketone in blood. Ketostix for measuring ketones in urine. Food diary will be used to collect food intake.

10.4 Describe any source records that will be used to collect data about subjects (e.g. school records, electronic medical records).

Response: electronic medical records and research files.

10.5 Indicate whether or not **individual** subject results, such as results of investigational diagnostic tests, genetic tests, or incidental findings will be shared with subjects or others (e.g., the subject's primary care physician) and if so, describe how these will be shared.

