## 17.0 Data Management and Analysis

17.1 *Describe the data analysis plan, including any statistical procedures. This section applies to both quantitative and qualitative analysis.*

Response: **DATA ANALYSIS**

This is a prospective study to evaluate ketogenic stress before and after 12 week treatment with dapagliflozin and exenatide/Bydureon. The similarities in baseline values between the study groups will be compared using appropriate parametric tests. Transformations of the data on order to meet statistical assumptions may be considered. All statistical analysis will be carried out using SPSS software (SPSS Inc, Chicago, Illinois) based on intention to treat principle. Data will be presented as mean± standard error. *Data will not be imputed to replace missing data and only observed data will used to run the mixed model for repeated measurement (MMRM) analysis. The primary endpoint of the study is to detect a significant difference in the percent change in beta-hydroxybutyrate and acetoacetic acid (total ketone bodies) in the plasma samples following 12 weeks of dapagliflozin treatment compared to placebo. *Fasting samples collected at weeks 0, 1, 4, 8 and 12 will be used for this comparison with values at week 0 considered as baseline. The statistical analysis will be done using MMRM with assigned  $\alpha$  value of 0.05. There is no previous data on effects of dapagliflozin alone on ketone bodies generation in T1D but our preliminary data on 12 weeks treatment with**

dapagliflozin in patients with T1D using insulin and liraglutide shows more than a 2 fold increase in total ketone bodies.

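### Secondary fasting endpoints are compared with placebo by repeated-measures ANOVA, which loses patients without week 12 data, although the primary endpoint from the same visits uses MMRM

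*Combined protocol and SAP*

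**What the plan says.** Section 17.1 states that all analyses are "based on intention to treat principle". It rules out imputation and says that "only observed data will used to run the mixed model for repeated measurement (MMRM) analysis". For the primary endpoint, fasting plasma ketone bodies on dapagliflozin against placebo, "Fasting samples collected at weeks 0, 1, 4, 8 and 12 will be used for this comparison", with week 0 as baseline, and "The statistical analysis will be done using MMRM with assigned" an alpha of 0.05.

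For the secondary endpoints the method changes. Basal plasma glucagon, FFA and urinary ketone bodies are compared "to placebo using 2-way RMANOVA". Insulin dose, glucose and carbohydrate intake are compared "to placebo with 2-way RMANOVA". The change from baseline within each arm is tested by paired t-test. The secondary text refers to change after 12 weeks and does not list the visits that enter the ANOVA.

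The data come from the same visits. Section 10.1 says "Fasting blood and 24hr urine samples will be collected at 1, 4 and 8 weeks", in addition to the week 0 and week 12 visits. Section 10.2 says "Measurements of beta-hydroxybutyrate, acetoacetic acid, glucose, FFA and glucagon, will be measured from all blood samples collected". Its table has insulin, glucose and diet records reviewed at each of these visits as well.

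Section 20.3 says that what was collected before a withdrawal will still be used.

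**The concern.** Classical repeated-measures ANOVA needs a complete set of values for each patient over the time points in the model. With imputation excluded, a patient without the week 12 value drops out of the comparison with placebo, and any values at weeks 1, 4 and 8 are not used. The plan gives no other rule for incomplete patients in this analysis, and its observed-data statement names only the MMRM.

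Two things are at stake. The first is consistency: an analysis of completers is not the intention-to-treat analysis that Section 17.1 promises, and it does not use withdrawn patients' data as Section 20.3 says. The second is bias. A completer analysis is generally safe only if data are missing completely at random. The withdrawal reasons in Section 20.1 include DKA, significant nausea, urinary and genital infections and pancreatitis. These may differ by arm, and some may be related to ketones, FFA or glucagon. MMRM needs only the weaker missing-at-random assumption.

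**Working it through.** **Inputs from the plan.** Difference 50%, SD 50%, alpha 0.05, power 80%, drop-out 15%, 20 per group (Section 17.2). Cohort 1 has 15 patients in each of four arms, and cohort 2 has no placebo arm (Section 4.1). Fasting visits are at weeks 0, 1, 4, 8 and 12.

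**The plan's own figure (primary endpoint).** Two-sided alpha is assumed, as sidedness is not stated.
- Normal approximation: n = 2 × (1.96 + 0.842)² × (50/50)² = 15.7, so 16 per arm; 16/0.85 = 18.8, so 19.
- With the t distribution: 16.7, so 17 per arm; 17/0.85 = 20.

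The stated 20 per group is reproduced. The plan gives no sample size or power for the secondary endpoints.

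**Patients left if only weeks 0 and 12 enter the ANOVA.** 15 × 0.85 = 12.75, about 12.8 per arm. A missed interim visit costs nobody on this reading. MMRM has the same 12.75 patients at week 12 and adds the earlier visits of those who left.

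**Patients left if all five visits enter.** Let m be the chance of missing each of weeks 1, 4 and 8 among those who reach week 12. The complete fraction is 0.85 × (1 − m)³. The values of m above zero are assumptions; the plan gives none.

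| m | Fraction | Complete, of 15 | Power at a 1-SD effect |
|---|---|---|---|
| 0 | 0.850 | 12.8 | 67.8% |
| 2% | 0.800 | 12.0 | 64.9% |
| 5% | 0.729 | 10.9 | 60.4% |
| 10% | 0.620 | 9.3 | 52.8% |

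The power column is a two-sample t-test with the primary endpoint's effect of 50/50 = 1 SD. It shows scale only.

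**Bias, as an illustration.** Simulation with 20 per arm, true week 12 difference 50, SD 50. In the active arm the 15% with the highest week 4 values leave before week 8; in the placebo arm 15% leave at random.

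| Correlation between visits | Completers only | Likelihood estimate (as in MMRM) |
|---|---|---|
| 0.3 | 46.1 | 50.1 |
| 0.5 | 43.9 | 50.4 |
| 0.7 | 40.8 | 49.9 |

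The standard deviations of the two estimates were close (17.3 v 17.7, 16.9 v 16.9, 16.8 v 16.5). When drop-out is the only loss, the gain from MMRM is therefore mainly in bias, and little in precision. The drop-out mechanism is assumed and is deliberately related to outcome.

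**The case against.** The strongest reply is that the secondary text speaks of change after 12 weeks, so the ANOVA may use weeks 0 and 12 only. The arm-by-time test is then a t-test on change scores, and a patient who misses week 1, 4 or 8 stays in. This reading is natural and nothing in the plan excludes it. A reader might infer that any missed visit removes a patient, or that the method imposes equal correlation on unequally spaced visits. Neither is supported, because the plan does not put the interim visits in this model. What remains on either reading is the loss of patients without week 12 and of their earlier data.

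It is also fair to say that exclusion of incomplete patients is not written in the plan. It follows from the named method together with the ban on imputation. Section 17.3 repeats the observed-data rule under quality control, but again only for the MMRM.

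A reader might further infer that Hypothesis 2 or the lipolysis endpoints as a group are compromised. Hypothesis 2 sets dapagliflozin against exenatide, whereas this ANOVA is against placebo. HSL and SGLT-2 are assigned to t-tests; among the lipolysis markers, the plan assigns only FFA to the ANOVA.

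Drug-related drop-out is possible but not shown to predominate. Withdrawal for DKA requires two unexplained episodes, and Section 20.1 also lists pregnancy, a change of insulin delivery and the patient's own decision.

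Finally, one could apply the assumed miss rate to all four post-baseline visits and get larger losses. That would charge week 12 a second time, since the 15% drop-out already covers it.

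**Conclusion.** The point holds for the fasting comparisons with placebo of glucagon, FFA, urinary ketone bodies, insulin dose, glucose and carbohydrate intake. The plan gives no reason for a method that handles missing data less well than the one it already uses at the same visits, and the result conflicts with Sections 17.1 and 20.3.

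The loss supported by the plan's own figure is 15%, which leaves about 12.8 of 15 per arm in cohort 1. Cohort 2 may add patients to the active arms but none to placebo. The lower counts of 10.9 and 9.3 need two assumptions: that all five visits enter the model, and that 5% or 10% of patients miss each interim visit. The size and direction of any bias depend on who leaves, which the plan cannot tell us.

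The primary analysis and its sample size, the acute AUC t-tests and the HSL and SGLT-2 t-tests are untouched. This is a worthwhile improvement to secondary analyses and no threat to the main conclusion.

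**What to change.** In Section 17.1, replace both 2-way RMANOVA comparisons with an MMRM on observed data at weeks 1, 4, 8 and 12. Specify arm, visit, arm-by-visit and the week 0 value as covariate, with an unstructured covariance and a named simpler structure if the model does not converge. Report the week 12 contrast of each active arm with placebo. The current primary-analysis text does not give the covariate, the covariance or the contrast, so these need to be written out.

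The cost is a change of wording. No new data are needed, and the plan already intends to fit an MMRM in the same software. MMRM does not protect against drop-out that depends on unobserved values, so reporting withdrawals by arm and reason alongside the results would help readers judge them.
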